## 5.1 Efficacy Evaluation

The effect of prednisone 60 mg (v. placebo) on WSP-induced airway and systemic inflammation will be assessed with the following measurements:

- a) sputum induction: sputum % PMNs (primary endpoint) and mucus production and composition
- b) gamma scintigraphy scan of radiolabeled Tc99 sulfur colloid: MCC
- c) sputum induction and EBC: airway inflammatory cytokines and markers of oxidative stress
- d) venipuncture: systemic inflammatory markers and cytokines

All measurements will be performed at baseline and again 4 hours post-WPS exposure, except for MCC which will be performed 2 hours post-WSP and will be completed by 4 hours post-WSP exposure. The change in these measurements (postWSP – preWSP) will be compared for each interventional arm (prednisone vs placebo). See Section 6 for detailed primary and secondary endpoints.

## **5.2 Pharmacokinetic Evaluation: n/a**

## **5.3 Safety Evaluations**

Safety evaluations will be performed with the following measures with strict adherence to subject withdrawal and study suspension criteria (Section 4.10):

- a) Physical exam and vital signs: In addition to a limited physical exam of the eyes, ears, nose, throat, and respiratory and cardiovascular systems, we will also check vital signs (temperature, HR, BP, RR, and oxygen saturations) at each baseline visit (0 and 5), pre-WSP and 4 hours post-WSP exposure (visits 3 and 7), and 24-hours post-WSP (visits 4 and 8). Additional exams and vital signs will be performed at physician discretion if needed based on the participant's symptoms.
- b) Spirometry: Spirometry will also be performed at each baseline visit (0 and 5), pre-WSP and 4 hours post-WSP exposure (visits 3 and 7), and 24-hours post-WSP (visits 4 and 8). Healthy volunteers have been shown to tolerate WSP exposure well without any changes in lung function (21). However, if participants assign a score greater than 3 ("moderate") to symptoms attributable to bronchospasm (cough, wheezing, chest tightness, shortness of breath, or pain on deep inspiration) following WSP exposure, then they will be evaluated by the study physician to determine if additional spirometry and/or rescue treatment with albuterol is necessary. Additional spirometry will be performed at physician discretion.
- c) Symptom questionnaire (see Appendix): This will be performed pre-WSP, immediately before exiting WSP chamber, and 4 hours post-WSP exposure (visits 3 and 7), and 24-hours post-WSP (visits 4 and 8). Symptoms may be accessed at other time points during the study per physician discretion.
- d) Direct observation: Participants will remain under the direct observation of a study coordinator and study physician throughout each study visit and will be monitored for a minimum of 5 hours following each WSP exposure.
- e) Post-study visit safety plan: We do not anticipate any delayed adverse events. However, all participants will have access to and contact information for a study

physician during the duration of their participation. Per study physician recommendations, they will be re-evaluated with an unscheduled visit as detailed in Sections 3.1 and 4.10. Additionally, all subjects will be contacted via phone by a study coordinator 3-7 days after visit 4 to access for any delayed adverse events as noted in Section 4.6 above.

## 6 STATISTICAL CONSIDERATION

### 6.1 Primary Endpoint

Change in sputum %PMNs [ $\Delta$  (postWSP – preWSP)[prednisone] vs  $\Delta$  (postWSP – preWSP)[placebo]] 4 hours post-WSP exposure **and at 24 hours post -WSP exposure**

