	
All measurements will be performed at baseline and again 4 hours post-WPS exposure, except for MCC which will be performed starting 2 hours after WSP exposure with measurements taken for a total of 120 minutes. Sputum induction will also be performed 24 hours post WSP challenge. The change in these measurements (postWSP – preWSP) will be compared for each interventional arm (prednisone vs placebo).

Safety Evaluations	
Vital signs, symptom questionnaire, spirometry

Statistical And Analytic Plan	
Our primary endpoint is the change in sputum %PMNs from baseline to 4 hours post-WSP exposure, comparing a single dose of prednisone to placebo. This analysis will rely on a linear mixed-effects model that accounts for the treatment effect and the period effect. Analysis of secondary endpoints (change in %PMNs 24 hours post WSP challenge, total mucin concentration, mucus composition, MCC, sputum and EBC inflammatory and oxidative stress markers, and systematic inflammatory markers, comparing a single dose of oral prednisone to matching placebo) will be performed similarly. The experiment-wide rate of Type I errors will be controlled at level <math>\alpha = 0.05</math>. Non-significant tests will be reported as being inconclusive.

DATA AND SAFETY MONITORING PLAN	
A study coordinator will enter data into REDCap, and then a second person will verify the data. Subjects will be monitored in real time for safety by study staff. A study physician will be immediately available during inhalation and treatment procedures and will determine the severity and relatedness of any adverse events (AEs). The PI will conduct ongoing assessment of safety with strict adherence to pre-specified study-suspension rules. All serious adverse events (SAEs) will be reported to UNC IRB and funding agency within 24 hours, and all AEs will be reported to UNC IRB and funding agency annually. A formal NC TracS Data Safety Monitoring Board (DSMB) charter meeting DOD approval will be established prior to commencing study. The DSMB will address issues regarding safety concerns, efficacy concerns, termination of the trial due to pre-specified stopping criteria, and ethical concerns. The DSMB will be furnished with relevant information by the Principal Investigator to make these decisions.

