### **2 STUDY OBJECTIVE**

#### **2.1 Primary Objective**

The primary objective of this study is to examine the effectiveness of a single oral dose of prednisone 60 mg (v. placebo) on mitigating WSP-induced airway inflammation, measured by sputum %PMNs, in healthy adults 4 hours post-WSP exposure.

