#### **6.4 Statistical Methods**

Our analytic plan was developed in collaboration with [name], the biostatistician for the CEMALB, who will oversee all statistical analyses. For analysis of our primary endpoint, change in sputum %PMNs at 4 hours post-WSP exposure, we will employ a linear mixed-effects model used in previous studies that allows us to assess treatment effect while accounting for any period effect (14, 16). The parameter estimates obtained by fitting this model (i.e., inter- and intra-subject variance, period effect, and treatment effect) will be used to compute estimates (e.g., effect sizes, means, standard errors, confidence intervals) and to compute a p-value for the primary null hypothesis that the difference in treatment effects is exactly zero in the target population. The same linear mixed-effects regression modeling technique will be used to analyze secondary endpoints as well. Additionally, we will use tabular and graphic methods to describe/explore the basic relationship between the treatment groups, including confidence intervals for all statistical estimates. Subsequently, as part of sensitivity analyses, we will compare the  $\Delta$  sputum %PMNs (post WSP – pre WSP [prednisone]) vs (post WSP – pre WSP [placebo]) using a paired-sample T-Test. Examination of the normality assumption will be performed, and a nonparametric Wilcoxon signed-rank test will be conducted in the case of evidence of extreme departure from normality. For all of the aforementioned analyses, criterion for significance will be  $p \leq 0.05$ , and results exceeding this threshold will be reported as inconclusive. Lastly, we will employ multiple variable regression modeling techniques to determine if specific individual risk factors (e.g., BMI) impact either the effect of WSP exposure or the effect of treatment on the primary or secondary endpoints, similar to approaches previously described to assess genotype effects on pollutant responses (23). These analyses will only be conducted after the primary hypothesis is tested and solely for exploratory purposes.

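### Section 6.1 makes sputum %PMN at both 4 h and 24 h primary, the rest of the plan names 4 h only, no rule combines the two, and the promised experiment-wide 0.05 has no procedure behind it

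*Combined protocol and SAP*

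**What the plan says.** **Primary endpoint.** Section 6.1 gives the change in sputum %PMN, prednisone against placebo, at 4 h "and at 24 hours post -WSP exposure". Section 5.1 directs the reader there: "See Section 6 for detailed primary and secondary endpoints".

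Other sections name 4 h alone:
- Synopsis, statistical plan: "Our primary endpoint is the change in sputum %PMNs from baseline to 4 hours post-WSP exposure". It then places the later time point elsewhere: "Analysis of secondary endpoints (change in %PMNs 24 hours post WSP challenge, total mucin concentration, mucus composition, MCC".
- Section 2.1: "measured by sputum %PMNs, in healthy adults 4 hours post-WSP exposure".
- Section 6.4: "For analysis of our primary endpoint, change in sputum %PMNs at 4 hours post-WSP exposure". The model is used to "compute a p-value for the primary null hypothesis that the difference in treatment effects is exactly zero in the target population", which is one hypothesis.
- Section 6.5 sizes the trial on the 4 h change.

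Three further statements tie the primary post-exposure sample to 4 h. The Synopsis design and Section 3.1 say the 4 h samples serve the primary and secondary analyses. Section 5.1 schedules the efficacy measurements other than MCC at baseline and 4 h.

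**Type I error.** Directly after listing the secondary endpoints, the Synopsis says: "The experiment-wide rate of Type I errors will be controlled at level" 0.05. Section 6.4 uses p ≤ 0.05 for all the analyses it has described, secondary endpoints included. It names no family, order or adjustment. Its only ordering is that the risk-factor models come after the primary test and are exploratory.

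**The concern.** A primary endpoint with two time points needs a rule: both significant, either significant, or one named as decisive. Section 6.1 has two time points and no rule; the remaining sections have one time point and need none. If 4 h is significant and 24 h is not, the trial is positive by 6.4 and undecided by 6.1. If only 24 h is significant, it is inconclusive by 6.4 and again undecided by 6.1. If this is settled after unblinding, the choice can follow the data.

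The Type I sentence raises a second, smaller problem. A reader of the Synopsis could take a significant secondary result as error-controlled when nothing in 6.4 makes it so.

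**Working it through.** **1. Inputs.** From 6.5: responder means of 24% at baseline, 40% at 6 h and 52% at 24 h; assumed 50% inhibition; 12 complete datasets. The documents give no SD, no power and no correlation between time points, so N = 12 cannot be reproduced and the results below are conditional. The allowance for loss can be checked: 12/(1 − 0.10) = 13.3, rounded up to the stated 14.

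**2. Effects implied by 6.5.**
- Earlier time point: (40 − 24) × 0.5 = 8 points. The source labels this 6 h; I use it for the 4 h endpoint, as 6.5 appears to.
- 24 h: (52 − 24) × 0.5 = 14 points.

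**3. Model.** Two-period cross-over with 12 subjects, 6 per sequence; two-sided t on 10 df; critical value 2.228 at 0.05 and 2.634 at 0.025. Noncentrality is 3.11 for 80% power and 3.60 for 90%. With equal SD at the two times (assumed), the 24 h noncentrality is 14/8 = 1.75 times the earlier one, so 24 h power is about 99.8% when earlier power is 80%. Results below are simulated.

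**4. How often exactly one time point is significant, and how often both are.**

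| Assumption | Exactly one, 80% at 4 h | Both, 80% | Exactly one, 90% at 4 h | Both, 90% |
|---|---|---|---|---|
| Effects 8:14, equal SD, correlation 0 to 0.9 | about 20% | about 80% | about 10% | about 90% |
| Equal effects, correlation 0 | 32% | 64% | 18% | 81% |
| Equal effects, correlation 0.5 | 24% | 68% | 14% | 83% |
| Equal effects, correlation 0.8 | 15% | 72% | 9% | 85% |

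In the 8:14 case nearly all the disagreement is a significant 24 h result with 4 h missed, so it is close to 1 minus the 4 h power at any correlation.

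**5. Primary Type I error by reading.**
- 4 h alone: 5%.
- Both required: at most 5%, approached when one time point has a very large effect and the other none.
- Either suffices: 1 − 0.95² = 9.75% if independent; about 9.2% at correlation 0.5 and 8.0% at 0.8.

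Independence is unlikely because both changes subtract the same pre-exposure sputum value. With equal variances and a common correlation ρ among the three samples, cov(Y4 − Y0, Y24 − Y0) = 1 − ρ and each variance is 2 − 2ρ (in units of the common variance), so the changes correlate 0.5.

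**6. Split alpha.** At 0.025 per time point, 4 h power falls from 80% to about 68%, or from 90% to about 81%.

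**The case against.** The strongest reply is that the text is not evenly divided. The objective, the design section, the efficacy schedule, the model, the single null hypothesis and the sample size all point to 4 h, and 6.1 stands alone. The parts that drive the analysis, 6.4 and 6.5, are clear. On that view the 24 h words are an editing slip in a small Phase I/II study.

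Most of this stands: 4 h is the better-supported reading. It does not close the matter. Section 6.1 is the formal definition, 5.1 sends readers to Section 6, and 6.5 reports a larger response at 24 h, which could be a reason to promote it. Nor can it be inferred that 6.1 is the later, governing text: the added words are in bold, but nothing dates them.

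Two stronger readings are tempting and unsupported:
- A reader might infer that the plan inflates the primary error rate to 8% to 10%. That needs success on either time point, which no passage states.
- A reader might attach a large experiment-wide error to the unadjusted secondary tests: 1 − 0.95⁸ = 34% for 8 independent tests, or 1 − 0.95¹⁰ = 40% for 10. Those counts have to be invented, because the documents do not enumerate the tests. Section 6.3 also labels exploratory several measures (mucus, MCC, EBC) that the Synopsis calls secondary. What the text supports is narrower: the promise is kept only if the family is the primary alone, and the plan does not say that it is.

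**Conclusion.** The inconsistency is real, lies in current text, and can change whether the trial is called positive. Its practical size is the chance that the two time points disagree. With 80% power at the earlier one, that is about 20% under the effect pattern in 6.5, or 15% to 32% with equal effects; with 90%, about 10%, or 9% to 18%. These figures rest on assumed power, on equal SD in the 8:14 case, and on correlations of 0 to 0.8 in the equal-effect case. No inflation of the primary error rate is shown under the readings the text supports. The experiment-wide sentence is a subsidiary matter: a commitment without a procedure, to be narrowed. Because the repair is nearly free now and not credible after unblinding, it should be made before unblinding.

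**What to change.** Before unblinding:
1. Make 6.1 agree with the Synopsis, 2.1, 6.4 and 6.5: 4 h is the sole primary, and 24 h %PMN is secondary.
2. Limit the Synopsis Type I sentence to the 4 h primary test.
3. State in 6.4 that secondary endpoints are reported with estimates, confidence intervals and nominal p-values, without a confirmatory claim.

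A fixed sequence that tests 24 h at 0.05 only after a significant 4 h result is optional; it costs nothing at 4 h.

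The cost is wording. The sample size stays at 12 complete datasets and 14 subjects, and 4 h power is untouched. The downside is that 24 h loses the primary label.

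If the sponsor does intend 24 h to be primary, state a both-required or split-alpha rule in 6.1 and 6.4 and redo 6.5 for it. Split alpha lowers 4 h power from 80% to about 68%. Requiring both costs little if the 24 h effect is as large as 6.5 implies (about 80% joint power), but gives 64% to 72% if the effects are equal.

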### 6.2 Secondary Endpoints

#### 1) Induced Sputum:

- a) Granulocyte (e.g.eosinophil) numbers/mg and percentages at 4 and 24 hours post-WSP exposure
- b) cytokine and chemokine concentrations ( $T_{H1}$  and  $T_{H2}$ ) via Mesoscale platform (pg/ml)

#### 6.3 Exploratory Outcome measures:

##### 1) Induced sputum:

- a) Oxidative stress markers [e.g. GSH/GSSG ratio, 8-isoprostanate(pg/ml)]
- b) Mucus-based parameters including: total mucin concentration ( $\mu\text{g}/\text{ml}$ ), % solid content, MUC5AC and MUC5B concentrations (pmol/ml) and ratio, biophysics (cohesion; macro- and micro-bead rheology)

##### 2) EBC:

- a) Sialic acid/urea ratio
- b) purine mediators ( $\mu\text{M}$ )
- c) amino acids and dipeptides ( $\mu\text{M}$ )
- d) GSH/GSSG ratio

##### 3) MCC measures:

- a) the central (C) vs. peripheral (P) deposition ratio (C/P), for regional airway deposition
- b) MCC, rate at which radiolabeled particles are cleared from the lung (reported as % particle retention vs time)
- c) skew, a measure of the particle deposition heterogeneity

##### 4) Blood:

- a) Systemic inflammatory markers (granulocyte numbers/mL and percentages)
- b) Serum cytokine concentrations via Mesoscale platform (pg/mL)

#### **6.4 Statistical Methods**

Our analytic plan was developed in collaboration with [name], the biostatistician for the CEMALB, who will oversee all statistical analyses. For analysis of our primary endpoint, change in sputum %PMNs at 4 hours post-WSP exposure, we will employ a linear mixed-effects model used in previous studies that allows us to assess treatment effect while accounting for any period effect (14, 16). The parameter estimates obtained by fitting this model (i.e., inter- and intra-subject variance, period effect, and treatment effect) will be used to compute estimates (e.g., effect sizes, means, standard errors, confidence intervals) and to compute a p-value for the primary null hypothesis that the difference in treatment effects is exactly zero in the target population. The same linear mixed-effects regression modeling technique will be used to analyze secondary endpoints as well. Additionally, we will use tabular and graphic methods to describe/explore the basic relationship between the treatment groups, including confidence intervals for all statistical estimates. Subsequently, as part of sensitivity analyses, we will compare the  $\Delta$  sputum %PMNs (post WSP – pre WSP [prednisone]) vs (post WSP – pre WSP [placebo]) using a paired-sample T-Test. Examination of the normality assumption will be performed, and a nonparametric Wilcoxon signed-rank test will be conducted in the case of evidence of extreme departure from normality. For all of the aforementioned analyses, criterion for significance will be  $p \leq 0.05$ , and results exceeding this threshold will be reported as inconclusive. Lastly, we will employ multiple variable regression modeling techniques to determine if specific individual risk factors (e.g., BMI) impact either the effect of WSP exposure or the effect of treatment on the primary or secondary endpoints, similar to approaches previously described to assess genotype effects on pollutant responses (23). These analyses will only be conducted after the primary hypothesis is tested and solely for exploratory purposes.

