### **3 INVESTIGATIONAL PLAN**

#### **3.1 Study Design**

- **Type of design:** Randomized, double-blind, placebo-controlled cross-over study
- **Study phases:**
  - a) Screening: Prior to enrollment in this study, participants will take part in two separate screening protocols: a general screening protocol (IRB #98-0779) and a screening WSP exposure protocol (IRB #15-1775). The general screening protocol will identify healthy volunteers suitable for WSP exposure. These healthy adults will undergo the screening WSP exposure protocol to identify those individuals with a  $\geq 10\%$  increase in sputum %PMNs following WSP exposure, who will then be invited to participate in this study.

- b) Visits 0, 1, and 2 – Baseline (Period 1) and Training Day: Along with an informed consent, a medical screening, including spirometry, will be performed to confirm eligibility. Volunteers will be trained on the cycle ergometer to reach an exercise level producing a minute ventilation of 20 L/min/m^2 body surface area (BSA) while being monitored with a 12 lead electrocardiogram (EKG) per our established WSP exposure procedure. Finally, a baseline MCC scan and sputum induction will be obtained, which will provide some of the “pre-WSP” measurements for primary and secondary data analyses. A 30 minute retention scan will be performed 24 hours after baseline MCC to determine amount of Tc99m-SC retained in airways.
- c) Visits 3 (Period 1) and 7 (Period 2) - WSP exposure: Participants will return within 4 weeks of Visit 0 to undergo WSP exposure. Spirometry, venipuncture, and EBC will be obtained prior to exposure. After WSP exposure, subjects will receive either a single dose of prednisone 60 mg or matching placebo. Four hours after WSP exposure, participants will then inhale radiolabeled Tc99m sulfur colloid (Tc99m-SC) to start MCC assessment. MCC measurements will be taken for a total of 120 minutes. EBC, venipuncture, and sputum induction will be obtained 4
- d) hours post-WSP exposure, which will provide the “post-WSP” measurements for primary and secondary data analyses. Spirometry and symptom questionnaires will be obtained pre- and post-exposure to assess for safety endpoints.
- e) Visits 4 (Period 1) and 8 (Period 2) - 24 hours post-exposure follow-up: Any symptoms post-WSP exposure will be reviewed and spirometry repeated along with EBC and sputum induction. Participants will undergo a 30-minute scan to determine amount of Tc99m-SC retained in airways.

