- f) Visits 5 and 6 – Cross-over and Baseline (Period 2): Participants will return after a minimum 4 week wash-out period, which is the amount of time allotted for resolution of airway inflammation post-WSP exposure. Interval medical history will be reviewed and repeat MCC, spirometry, and sputum induction obtained as pre-WSP measurements for period 2. A retention scan will be performed 24 hours after baseline MCC for period 2. Participants will then be crossed over to the alternative treatment group and undergo visits 7 and 8 as above.
- g) Visit 9 – Study Completion: Five to 10 days after the second exposure, participants will return for a study completion visit in which medical history and symptom questionnaires will be reviewed. If the participant has any health symptoms or concerns, they will receive a physical examination and evaluation by a study physician.
- h) Unscheduled Visits: We do not anticipate any unscheduled visits. However, subjects will be provided with contact information for a study physician in the event of any delayed adverse events outside of direct observation during study visits and re-evaluated as deemed necessary by the study physician. Subjects will be rescheduled if they have a change in health status that requires a delay in study

visits. If this causes a visit to be out of window, the subject can have an unscheduled visit at the discretion of the PI.

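### Should the primary model for sputum %PMNs estimate a baseline slope instead of analysing change scores with treatment and period terms only?

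*Combined protocol and SAP*

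**What the plan says.** The Synopsis describes the primary analysis in one sentence: "This analysis will rely on a linear mixed-effects model that accounts for the treatment effect and the period effect". Section 6.4 names the change in sputum %PMNs at 4 hours as the response, states that "we will employ a linear mixed-effects model used in previous studies that allows us to assess treatment effect while accounting for any period effect", and lists what the fit will yield: "The parameter estimates obtained by fitting this model (i.e., inter- and intra-subject variance, period effect, and treatment effect"). A baseline slope is not on that list. Section 5.1 frames every efficacy comparison in the same way: "The change in these measurements (postWSP – preWSP) will be compared for each interventional arm (prednisone vs placebo"). The supporting analyses in 6.4 are a paired t-test on the same change scores and, if needed, a rank test: "a nonparametric Wilcoxon signed-rank test will be conducted in the case of evidence of extreme departure from normality".

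The pre-exposure sputum does not come from the exposure day. For period 1, section 3.1 places it at the baseline and training visits, where "a baseline MCC scan and sputum induction will be obtained"; section 4.3 puts it at Visit 1. For period 2 it comes from Visit 5, with "repeat MCC, spirometry, and sputum induction obtained as pre-WSP measurements for period 2". On the exposure days (Visits 3 and 7) the listed pre-exposure tests do not include sputum: "Spirometry, venipuncture, and EBC will be obtained prior to exposure". The Appendix table agrees.

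Section 6.5 gives responder means of 24% before exposure and 40% afterwards (labelled 6 hours), assumes that prednisone halves the rise, and arrives at 12 complete datasets from 14 subjects. It states neither an SD nor a power.

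**The concern.** A change score without a baseline term fixes the slope of post on pre at 1. In a cross-over, a subject's stable level already cancels between periods. Subtracting a period-specific baseline therefore helps only as far as a temporary deviation at Visit 1 or Visit 5 is still present on the exposure day, possibly weeks later. If little of it persists, the subtraction adds the noise of a second sputum sample to each period.

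The stake would be power. The target fell from 20 to 12 complete datasets, and any p-value above 0.05 is to be reported as inconclusive. None of the planned supporting analyses relaxes the slope of 1. The model is also described partly by reference to earlier studies, so a reader might wonder whether a baseline term was intended.

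**Working it through.** **The plan's own figure.** The step from 12 to 14 reproduces: 12/(1 − 0.10) = 13.3, rounded up to 14. The 12 itself cannot be reproduced, because 6.5 gives no SD and no power. The check therefore works back from 12.

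**Inputs**
- Effect: 0.5 × (40 − 24) = 8 points (6.5; the 6-hour mean stands in for 4 hours).
- n = 12, taken as 6 per sequence; two-sided 0.05 (assumed, as sidedness is not stated).
- Change-score power of 80% (assumed). With treatment and period terms (10 df), this implies an SD of 8.91 for the within-subject difference of changes and a noncentrality of 8 × √12 / 8.91 = 3.11. At 90% the SD is 7.69.

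**Formulas.** Let r be the correlation between a subject's between-period differences in pre and post values, and k the ratio of their SDs (post/pre).
- Change-score variance ∝ 1 + k² − 2rk.
- Adjusted variance ∝ k²(1 − r²).
- Ratio R = 1 + (1 − rk)² / [k²(1 − r²)].
- Estimating the slope leaves 9 df and inflates the variance by a factor 1 + χ²(1)/χ²(10), with mean 1 + 1/8 = 1.125. Adjusted power is the noncentral t power averaged over that factor.

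Two cases show the range. With k = 1 and r = 0, R = 2, the noncentrality is about 3.11 × √(2/1.125) = 4.15, and power is 95%. With rk = 1, R = 1, the noncentrality is about 3.11 × √(1/1.125) = 2.93, and power is 74.7%, the floor.

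**Anchoring k.** The documents give no SD ratio, so four variance patterns were assumed at means 24 (pre), 40 (placebo) and 32 (prednisone):
- constant SD: k = 1;
- binomial type: √{[(0.40×0.60 + 0.32×0.68)/2] / (0.24×0.76)} = 1.12;
- constant on the logit scale: √{[(0.40×0.60)² + (0.32×0.68)²]/2} / (0.24×0.76) = 1.26;
- proportional to the mean: √[(40² + 32²)/2] / 24 = 1.51.

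**Adjusted power (%) when change scores have 80%**

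| k | r = 0 | 0.3 | 0.5 | 0.7 | 0.9 | Adjustment ahead when |
|---|---|---|---|---|---|---|
| 1.00 | 95 | 90 | 85 | 81 | 77 | r below about 0.75 |
| 1.12 | 94 | 87 | 82 | 78 | 75 | r below about 0.58 |
| 1.26 | 91 | 84 | 79 | 75 | 77 | r below about 0.46 or above 0.93 |
| 1.51 | 88 | 80 | 76 | 75 | 85 | r below about 0.30 or above 0.86 |

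Change scores hold their own over more than a narrow band of slopes around 1. At k = 1.51 they are ahead for slopes rk from about 0.45 (0.30 × 1.51) to 1.3 (0.86 × 1.51).

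**Average over the unknowns.** On a uniform grid of k from 1 to 2 and r from 0 to 0.95, adjusted power exceeds 80% in 48% of cells, with a mean of 81%. If change-score power is 90%, the floor is 85.7%, no gain can exceed 10 points, adjustment is ahead in about 46% of cells, and the mean is 90.3%.

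**Validity.** In simulations of 40,000 trials per setting, covering normal, heavy-tailed, skewed and bounded data, Type I error was 3.6 to 5.3% for both analyses.

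**The case for a change.** The best case for a change rests on asymmetry: adjustment risks about 5 points of power to gain up to about 15, and a baseline from an earlier visit makes a low r believable. It would need only wording, and 6.5 says that no samples had been analysed when the target was revised, so the choice could be made blind. The model is also never written out as an equation.

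Part of this stands. If r is about 0.3 or less and k lies between 1 and 1.5, estimating the slope is at least as good and often better. But low r is an assumption. The anchors for k come from group means, whereas the k that matters belongs to within-subject differences between periods, on which those means are silent. The asymmetry also shrinks if the true starting power is above 80%. With 12 differences, one unusual sample can move an estimated slope. A mixed model with baseline and subject-mean baseline does not always reduce to the simple regression of differences on 9 df: when the subject variance is estimated at zero, the error term and its degrees of freedom change.

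On the missing equation, the endpoint, the listed parameters, section 5.1 and the sensitivity tests all point to a mixed model on change scores with treatment, period and a random subject effect. An analyst would fit that. The reference to earlier studies leaves a small opening that cannot be checked from these documents, but nothing in the text invites a baseline term.

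**Conclusion.** No change is needed. The reading of the plan is correct: the slope is fixed at 1 for a sputum baseline from an earlier visit. The analysis nonetheless gives a valid, unbiased test of the stated endpoint and agrees with the planned sensitivity analyses. Whether an estimated slope would do better depends on r and k, which the documents do not give. Under the assumptions used here (12 complete datasets, an 8-point effect, 80% change-score power, k between 1 and 1.51, r from 0 to 0.9), the difference runs from a gain of about 15 points to a loss of about 5, with no clear advantage on average. Experienced statisticians could reasonably choose either model at this sample size. The unwritten equation is missing detail that the rest of section 6.4 lets an analyst fill sensibly.
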